8.6. Pharmacokinetics

During the initial induction cycle, plasma samples (~2 mL) will be collected for analysis of dociparstat concentrations to derive pharmacokinetic parameters, as data permit.

Plasma samples will be collected at the following time points:

- Day 1: predose; at the end of the IV bolus; and at 1 hour and 12 hours after the end of the IV bolus.
- Day 4: a single sample will be collected during the infusion (ideally in the morning).
- Day 8: within ~5 minutes after the end of the infusion, and at 0.5, 1, 2, and 4 hours after the end of the infusion.

Blood samples will ideally be collected within ± 10 minutes of the specified time points. The date and actual time (24-hour clock time) **must be recorded** for each blood sample. The timing of sampling may be altered during the study based on newly available data and up to 3 samples may be collected at additional time points (if warranted and agreed upon between the investigator and the sponsor) to ensure appropriate monitoring.

Note: Do not draw blood from the same line that is used for study intervention administration. Drawing blood from a heparinized line may falsely alter the PK results obtained; therefore, if

using an indwelling catheter, draw approximately 5 mL of blood for discard before drawing the PK sample. Additional information regarding sample collection and handling is provided in the laboratory manual.

Drug concentration information that would unblind the study will not be reported to investigative sites or blinded personnel until the study has been unblinded.

Pharmacokinetic parameters to be evaluated include area under the concentration-time curve (AUC), maximum observed concentration (Cmax), time to maximum observed concentration (Tmax), terminal elimination half-life (t_{1/2}), and clearance. Plasma samples collected for analyses of dociparstat concentrations may also be used to evaluate safety or efficacy aspects related to concerns arising during or after the study.

Genetic analyses will not be performed on these plasma samples. Participant confidentiality will be maintained.

PK samples will be collected at study centers with appropriate capabilities (e.g., centrifuge, staff experience and availability).

8.7. Pharmacodynamics

Pharmacodynamic parameters are not evaluated in this study.

8.8. Genetics

Genetic variation may impact a participant's response to study intervention and susceptibility to, severity of, and progression of disease. An optional saliva specimen or buccal swab will be obtained for germ-cell line analysis. Variable response to study intervention may be due to genetic determinants that impact drug absorption, distribution, metabolism, and excretion; mechanism of action of the drug; disease etiology; and/or molecular subtype of the disease being treated.

Cytogenetic Analyses

Cytogenetic testing of bone marrow samples is a required screening test to appropriately type and characterize AML and to determine eligibility for study enrollment based on intermediate or adverse/unfavorable genetic risk.

Biobanking

Where local regulations and IRB/IEC allow, a 10-mL bone marrow sample and a 10-mL whole blood sample will be collected at designated time points for biobanking from participants who have consented to participate in this component of the study.

- Whole blood and bone marrow will be processed at the central lab to isolate cells for cryopreservation to maintain viability.
- Retrospective analysis on cryopreserved cells and/or extracted nucleic acids from biobanked samples will be conducted for research related to biomarkers of response/resistance to study drugs and mechanism of action for dociparstat. This could allow for developing tests/assays to predict response and resistance to the study drugs, including dociparstat.

- The results of genetic analyses may be reported in the clinical study report or in a separate study summary report.
- The sponsor will store the samples (cells, DNA or RNA) in a secure storage space with adequate measures to protect confidentiality.
- The samples will be retained while research on dociparstat continues, but no longer than 15 years or other period as per local requirements.

Participation in biobanking is strongly encouraged, but optional. Participants who do not wish to participate in biobanking may still participate in the study.

Details on processes for collection, shipment, and destruction of these samples is included in the laboratory manual.

8.9. Biomarkers

- For all participants, bone marrow aspirate/biopsy samples will be collected and tested for MRD via MFC at screening and after hematologic recovery for each cycle of induction and consolidation chemotherapy (as specified in the Schedule of Activities) to evaluate the association with dociparstat treatment and the observed OS and EFS.
- Blood samples will be collected during induction and consolidation therapy to measure plasma levels of HMGB1, which is expressed in tumor tissues and higher levels have been correlated with worse clinical prognosis. The association of dociparstat with lower HMGB1 levels will be evaluated. See Section 1.2 for collection timepoints. For participants who receive multiple consolidation cycles, only samples from the last consolidation cycle will be analyzed. Blood samples collected for HMGB1 may be reserved for batch analysis. Refer to the laboratory manual for instructions on collection of a separate sample, versus using blood from the biobanked sample for analysis.
- Biobanked blood and bone marrow may be used to conduct retrospective analyses of biomarkers including, but not limited to, CXCR4, CXCR7, CXCL12, and LSC markers to evaluate their association with observed clinical responses and gain insight into the mechanism of action of dociparstat in AML treatment. Genetic markers known to be related to AML response and or resistance (e.g., clonal selection for TP53 and FLT3 variants) may be examined and additional analyses may be conducted to advance understanding of potential predictors for response (e.g., gene signatures associated with LSCs).

Details on processes for collection, shipment, and destruction of these samples is included in the laboratory manual.

Table 9: Sample Collection Time Points for MRD Analyses and for Biobanking

Sample Time	Analysis	Sample Material
Screening	MRD + Biobanking	10 mL Bone marrow 10 mL Whole blood
Recovery after initial induction (Day ~28-42)	MRD + Biobanking	10 mL Bone marrow 10 mL Whole blood
Recovery after reinduction (Day ~28-42)	MRD + Biobanking	10 mL Bone marrow 10 mL Whole blood
After each consolidation cycle	MRD + Biobanking	10 mL Bone marrow 10 mL Whole blood
Relapse	MRD + Biobanking	10 mL Bone marrow 10 mL Whole blood

8.10. Medical Resource Utilization

Dates of hospitalization and discharge, and number of days spent in intensive care settings will be assessed. Number of blood product units (e.g., red blood cell transfusions, platelet transfusions) administered and number of growth factor administrations will also be collected.

9. STATISTICAL CONSIDERATIONS

9.1. Statistical Hypotheses

The null hypothesis is that the effect of dociparstat plus standard chemotherapy on OS and EFS equals the effect of standard chemotherapy, or:

$$H_0: S_{dstat} = S_{pbo}$$

The alternative hypothesis is that the effect of dociparstat plus standard chemotherapy on OS and EFS does not equal the effect of standard chemotherapy, or:

$$H_A: S_{dstat} \neq S_{pbo}$$

9.2. Sample Size Determination

Approximately 1000 potential participants are expected to be screened to achieve a total of approximately 570 participants randomly assigned to study intervention.

Sample size calculations were based on the OS primary and EFS key secondary endpoints. Randomized Phase 2 data in the subset of participants matching our proposed Phase 3 population show an observed OS HR of 0.51 and control median OS of 16.1 months; however, these estimates are associated with substantial uncertainty given the small size of the Phase 2 study as well as actual and potential emerging post-induction and post-relapse therapies for patients with AML. To account for these factors, we assume a clinically-meaningful OS HR of 0.7 and a control median OS of 18 months; this corresponds with a dociparstat median OS of 25.7 months. Hence, assuming 24-month accrual, 24-month minimum follow-up time, and accounting for one formal interim analysis (see Section 9.5), the planned sample size will have >85% power to demonstrate a difference between treatment arms at a two-sided type I error rate of 4%. The target number of OS events is 308.

Similarly, we assume a clinically-meaningful EFS HR of 0.7, and a control median EFS of 10 months, 24-month accrual, and 24-month minimum follow-up. Hence, the planned sample size will have >85% power to demonstrate a difference between treatment arms at a two-sided type I error rate of 1%. Under the assumptions of 50% CR rates in both groups and no separation of the curves during the first 6 months, this is expected to result in 454 events.

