9.3. Analysis Sets

The following analysis sets are defined:

Analysis Set	Description
Screened	All participants who sign the ICF.
Intent to Treat (ITT)	All participants who are randomized. Participants will be analyzed in the group to which they were randomized.
Safety	All participants who are randomized to and receive at least one dose of blinded dociparstat or placebo. Participants will be analyzed in the group corresponding to the first blinded dose of study intervention received.

Analysis Set	Description
Per protocol (PP)	All participants who are randomized to and receive at least one dose of blinded dociparstat or placebo, excluding those who have any significant inclusion/exclusion criteria violation or noncompliance that would be expected to impact the analysis of efficacy. Participants will be analyzed in the group corresponding to the first blinded dose of study intervention received.

The ITT analysis set will be used to summarize all efficacy endpoints. The PP analysis set will be determined prior to unblinding and will be used for supportive primary and key secondary efficacy analyses and possibly other selected endpoints to be defined in the Statistical Analysis Plan (SAP). The safety analysis set will be used for all safety and all other non-efficacy (e.g., medical history, medications, exposure) analyses.

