9.4.1. Primary Endpoint

The primary OS inferential analysis will utilize the ITT analysis set and a log-rank test at two-sided alpha 0.04 stratified by baseline FLT3 status, cytogenetic risk, and age. Kaplan-Meier (KM) methods/plots and Cox models will be used. Log-rank p-values and hazard ratios with 95% CIs will be presented for each treatment comparison. Median failure times, KM estimates every 90 days, and corresponding 95% CIs will be presented for each group. Survival time will be measured from randomization. Participants who are not known to have died will be censored at the time they were last known to be alive. The final primary analysis will be conducted after approximately 308 death events have been observed.

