9.4.2. Key Secondary Endpoint

The key secondary EFS endpoint will be tested using the same method as the primary endpoint at two-sided alpha 0.01. A participant with any bone marrow CR assessment between Days 22 and 42, inclusive, after start of induction or reinduction treatment will be considered an induction success; relapse and death events will be assessed following the last CR assessment during this time period. A participant with no CR assessments during this window will be considered an induction failure and imputed as such at randomization. Participants with induction success and no observed relapse or death events will be censored at the time they were last known to be alive. Maximum neutrophil and platelet counts within 7 days before or after the bone marrow draw will be used to determine count recovery. The key secondary analysis will be supplemented by a planned sensitivity analysis (not subject to alpha control), in which participants progressing to hematopoietic cell transplant will be censored at the time of transplant. The key secondary analysis will be conducted at the same time as the final primary OS analysis.

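### The EFS power, median and event count in Section 9.2 do not match the EFS analysis in Section 9.4.2, which dates every induction failure at randomization.

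*Combined protocol and SAP*

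**What the plan says.** Section 9.2 sets the EFS inputs: "we assume a clinically-meaningful EFS HR of 0.7, and a control median EFS of 10 months", with 24-month accrual and 24-month minimum follow-up. From these it concludes that "the planned sample size will have >85% power to demonstrate a difference between treatment arms at a two-sided type I error rate of 1" percent. The next sentence changes the model: "Under the assumptions of 50% CR rates in both groups and no separation of the curves during the first 6 months". On that second basis the plan gives its event count: "this is expected to result in 454 events".

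The analysis is defined elsewhere. Section 9.3: "The ITT analysis set will be used to summarize all efficacy endpoints". Section 9.4.2: "A participant with no CR assessments during this window will be considered an induction failure and imputed as such at randomization". On timing, 9.4.2 says "The key secondary analysis will be conducted at the same time as the final primary OS analysis", and 9.4.1 says "The final primary analysis will be conducted after approximately 308 death events have been observed".

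The documents do not say whether 0.7 is a constant, post-lag or average hazard ratio, or whether it applies to all EFS events or only to events among responders. They give no event-time distribution for responders and no dropout rate.

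**The concern.** The sample-size paragraph and the analysis rule describe different survival curves. A 10-month median with proportional hazards implies a smooth decline from 1. The rule in 9.4.2, combined with 50% CR, implies that half of each arm has an event on day 0, equally in both arms. Those tied events carry no treatment difference but add variance to the log-rank statistic.

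The stated power is what the plan expects in return for giving EFS 1% of the 5% alpha. EFS can also trigger unblinding to the sponsor at the second interim analysis (9.5), and it affects the alpha for the later secondary tests (9.4.3). If true power is well below 85%, a non-significant EFS result tells the reader less than the protocol suggests.

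**Working it through.** **Inputs.** From 9.2: 570 participants, 1:1 (285 per arm); EFS HR 0.7, so |ln 0.7| = 0.3567; control median 10 months; two-sided alpha 0.01 (critical value 2.576); accrual 24 months; last look at month 48; OS control median 18 months, HR 0.7. Assumptions added here: uniform accrual, exponential times, no dropout. Stratification and the interim EFS look are not modelled.

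**1. The plan's power, reproduced.** With constant HR, no lag and no time-0 failures, power = Φ(√D/2 × 0.3567 − 2.576).
- Month 48, D = 491: √491/2 × 0.3567 = 3.95; power about 92%.
- 308 deaths, D = 423: 3.67; power about 86%.
- D = 454: 3.80; power 89%.

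So the claim holds on this model.

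**2. The median under 9.4.2.** Control EFS just after time 0 = 1 − 0.50 = 0.50. The usual median is the first time the curve is at or below 0.50, which here is time 0. Even at 51% CR, 0.50/0.51 = 0.980, so the median is reached once about 2% of responders have had an event.

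**3. Analysis time.** Expected deaths at month t = 285 × Σ[1 − (e^(−λ(t−24)) − e^(−λt))/(24λ)] over the two arms, with λ = ln 2/18 = 0.0385 (control) and 0.7 × 0.0385 = 0.0270.
- Month 48: 285 × (0.741 + 0.614) = about 386 deaths.
- 308 deaths are reached near month 36.8, about 11 months before the horizon in 9.2.

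**4. Power with half of each arm failing at time 0.** The hypergeometric variance of the time-0 block is V0 = 285 × 0.25 × 285/569 = 35.7.
- *0.7 as the log-rank average over all participants.* At 454 events, 454 − 285 = 169 occur later, so V = 35.7 + 169/4 = 77.9. Z = √77.9 × 0.3567 = 3.15, and power = Φ(3.15 − 2.576) = about 72%. For 85%, V must be (2.576 + 1.036)²/0.3567² = about 102.6, so (102.6 − 35.7) × 4 = about 268 of 285 responders need an event, or 553 of 570 participants in all.
- *0.7 as the responder HR, no lag.* For assumed responder medians from 23 down to 10 months, power is about 19–36% at month 48 and 12–28% at 308 deaths. With the 6-month lag added it is about 9–11% and 5–7%.
- *0.7 as a Cox HR with Efron or Breslow ties.* Simulated power at month 48 is 97–99%, but the responder HR must then be about 0.32–0.44 without the lag, or 0.12–0.18 with it.

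**5. The 6-month lag by itself** (control median 10 months, no time-0 failures):

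| Meaning of 0.7 | Post-lag HR | Month 48 | 308 deaths |
|---|---|---|---|
| Post-lag HR | 0.70 | 44% | 30% |
| Log-rank average | 0.55 / 0.51 | 90% | 85% |
| Ratio of medians, 10 vs 14.3 months | (10 − 6)/(14.3 − 6) = 0.48 | 98% | 89% |

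**6. Event count.** A 10-month exponential control median gives 491 events (constant HR) or 497 (lag, then 0.7) at month 48, and 423 or 433 at 308 deaths. Neither time gives 454.

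**The case against.** The CR and lag assumptions are attached grammatically to the event count, not to the power, and the power reproduces on the inputs that precede it. That is so. But both figures describe the same test on the same data, so one set of assumptions has to drive both.

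A reader might infer that the 6-month lag alone cuts power to about 44%, or 30% at 308 deaths. The documents do not support this. That figure needs 0.7 to be the hazard ratio after month 6, which 9.2 never says. Section 9.2 links HR 0.7 to a pair of medians for OS (18 and 25.7 months) and introduces EFS as similar, so the ratio of medians is at least as natural a reading. On that reading, or with 0.7 as the log-rank average, the lag leaves power at about 85% or more.

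The event count is weak evidence. An unstated dropout rate could account for 454, so the mismatch points to a missing input rather than a proven error.

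On the median, another convention would allow any value on a flat stretch at exactly 0.50. Ten months would then require that no responder has an event before month 10, which is not a credible design assumption.

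The responder medians of 10–23 months are assumptions made for this check. They show a range and do not estimate the trial's power. None of these objections reconciles the time-0 failures with a 10-month median, or month 48 with the 308-death trigger.

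**Conclusion.** The concern holds as a mismatch between the stated EFS figures and the plan's own endpoint rule and analysis trigger. The 10-month ITT control median cannot stand beside 50% CR with failures dated at randomization. The power above 85% is not shown for the analysis that will be run. With time-0 failures and equal CR rates, it is about 72% at 454 events on the all-participant log-rank reading and far lower on the responder reading. A Cox reading with ties can exceed 85%, but only with a much stronger responder effect than 0.7.

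It does not follow that EFS is certainly underpowered. The plan leaves the meaning of 0.7 and the responder distribution open, so true power cannot be fixed from the documents. OS power, the 308-death target and type I error are unaffected.

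**What to change.** Rewrite the EFS paragraph of 9.2 around one model that matches 9.4.2. It should state:
- the CR rate in each arm, and that participants without CR are events at randomization;
- the event-time distribution among responders;
- what HR 0.7 refers to: all EFS events (and with which tie handling) or responders only;
- whether the 6-month lag applies;
- any dropout rate;
- the analysis time, meaning the trigger of about 308 deaths, reconciled with the 24-month minimum follow-up.

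Then restate by simulation the control median, the expected EFS events and the power at that time. If more than 85% is kept, state the responder effect it requires.

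The cost is one simulation and revised wording in the protocol and SAP. The restated EFS power may be less favourable. No participants are added, and the OS design and the alpha split stay as they are.

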9.3. Analysis Sets

The following analysis sets are defined:

Analysis Set	Description
Screened	All participants who sign the ICF.
Intent to Treat (ITT)	All participants who are randomized. Participants will be analyzed in the group to which they were randomized.
Safety	All participants who are randomized to and receive at least one dose of blinded dociparstat or placebo. Participants will be analyzed in the group corresponding to the first blinded dose of study intervention received.

Analysis Set	Description
Per protocol (PP)	All participants who are randomized to and receive at least one dose of blinded dociparstat or placebo, excluding those who have any significant inclusion/exclusion criteria violation or noncompliance that would be expected to impact the analysis of efficacy. Participants will be analyzed in the group corresponding to the first blinded dose of study intervention received.

The ITT analysis set will be used to summarize all efficacy endpoints. The PP analysis set will be determined prior to unblinding and will be used for supportive primary and key secondary efficacy analyses and possibly other selected endpoints to be defined in the Statistical Analysis Plan (SAP). The safety analysis set will be used for all safety and all other non-efficacy (e.g., medical history, medications, exposure) analyses.

9.4. Statistical Analyses

All analyses will be presented by randomized group (dociparstat, placebo), unless otherwise specified. The SAP will be finalized prior to the first interim analysis. It will include a more technical and detailed description of the statistical analyses described in this section, which is a summary of the planned analyses of the most important endpoints, including primary and key secondary endpoints.

9.4.1. Primary Endpoint

The primary OS inferential analysis will utilize the ITT analysis set and a log-rank test at two-sided alpha 0.04 stratified by baseline FLT3 status, cytogenetic risk, and age. Kaplan-Meier (KM) methods/plots and Cox models will be used. Log-rank p-values and hazard ratios with 95% CIs will be presented for each treatment comparison. Median failure times, KM estimates every 90 days, and corresponding 95% CIs will be presented for each group. Survival time will be measured from randomization. Participants who are not known to have died will be censored at the time they were last known to be alive. The final primary analysis will be conducted after approximately 308 death events have been observed.

9.4.2. Key Secondary Endpoint

The key secondary EFS endpoint will be tested using the same method as the primary endpoint at two-sided alpha 0.01. A participant with any bone marrow CR assessment between Days 22 and 42, inclusive, after start of induction or reinduction treatment will be considered an induction success; relapse and death events will be assessed following the last CR assessment during this time period. A participant with no CR assessments during this window will be considered an induction failure and imputed as such at randomization. Participants with induction success and no observed relapse or death events will be censored at the time they were last known to be alive. Maximum neutrophil and platelet counts within 7 days before or after the bone marrow draw will be used to determine count recovery. The key secondary analysis will be supplemented by a planned sensitivity analysis (not subject to alpha control), in which participants progressing to hematopoietic cell transplant will be censored at the time of transplant. The key secondary analysis will be conducted at the same time as the final primary OS analysis.

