7.3. Participant Withdrawal from the Study

- It is expected that all participants randomized in the study, regardless of completion or discontinuation of study intervention, will remain in the study for long-term follow-up.
- Before withdrawing a participant from the study, clarify and document the specific expectations of the participant's request for withdrawal. The following withdrawal scenarios may apply:
 - Discontinuation of study intervention, but completes remaining study assessments, and agrees to collection of relevant follow-up information (i.e., remains in the study; this is the default scenario).
 - Discontinuation of study intervention and/or refuses further study-specific assessments, but agrees to collection of relevant follow-up information (i.e., remains in the study).
 - Completion or discontinuation of study intervention and/or refuses further assessments, AND withdraws consent for any further study communication or

follow-up from the study center (i.e., withdraws from the study); the investigator must document this in the site study records.

- A participant may withdraw from the study at any time at his/her own request, or may be withdrawn at any time at the discretion of the investigator for safety, behavioral, compliance, or administrative reasons.
- At the time of withdrawing from the study, if possible, an early withdrawal visit will be conducted. See the Schedule of Activities/Assessments (Section 1.2) for data to be collected at the time of study withdrawal and follow-up and for any further evaluations that need to be completed.
- If the participant withdraws consent for disclosure of future information, the sponsor may retain and continue to use any data collected before such a withdrawal of consent.
- If a participant withdraws from the study, he/she may request destruction of any samples taken and not tested; the investigator must document this in the site study records.

Discontinuation of specific sites or of the study as a whole are discussed in [Appendix 1](#).

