Cumulative incidence of relapse	
Defined through 5 years after randomization only for participants achieving CR (or CR/CRi) during induction/reinduction.
 
Measured from the date of randomization to the date of relapse. Participants not known to have relapsed will be censored on the date they were last known to be alive. Participants who die without relapse will be counted as competing-risk events.

Overall survival (OS) *Primary Endpoint	
Defined for all study participants through 5 years after randomization.
 
Measured from the date of randomization to date of death from any cause.
 
Participants not known to have died at last follow-up contact will be censored on the date they were last known to be alive.

Event-free survival (EFS) following CR *Key Secondary Endpoint	
Defined for all study participants through 5 years after randomization.
 
Measured from the date of randomization to treatment failure, relapse, or death from any cause, whichever occurs first. For this endpoint, treatment failure is defined as failure to achieve CR within 42 days of the start of induction/reinduction. Participants not known to have relapsed or died will be censored on the date they were last known to be alive.

EFS following CRi	
Defined for all study participants through 5 years after randomization.
 
Measured from the date of randomization to treatment failure, relapse, or death from any cause, whichever occurs first. For this endpoint, treatment failure is defined as failure to achieve CRi within 42 days of the start of induction/reinduction. Participants not known to have relapsed or died will be censored on the date they were last known to be alive.

Relapse-free survival (RFS)	
Defined through 5 years after randomization only for participants achieving CR (or CR/CRi) during induction/reinduction.
 
Measured from the date of randomization to date of relapse or death from any cause. Participants not known to have relapsed or died at last follow-up contact will be censored on the date they were last known to be alive.

Time to recovery of neutrophil count	
Defined for all study participants.
 
Measured as time from date of randomization until the first day the ANC is $>500/\mu\text{L}$ and is $>1000/\mu\text{L}$ following induction or reinduction (if indicated).

Response / Outcome	Definition

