Relapse	Relapse (hematologic)	After achievement of CR/CRi, bone marrow blasts $\geq 5\%$, reappearance of blasts in the blood, or development of extramedullary disease.
	Cumulative incidence of relapse	Measured from the date of randomization until the date of relapse. Participants not known to have relapsed will be censored on the date of last follow-up contact.
Outcome Measure	Overall survival (OS)	Measured from the date of randomization to date of death from any cause.
	Event-free survival	Measured from the date of randomization to treatment failure, relapse, or death from any cause, whichever occurs first.
	Relapse-free survival (RFS)	Measured from the date of randomization to date of relapse or death from any cause.
	Time to recovery	Time to recovery of neutrophil count is measured as time from date of randomization until the first day the ANC is $>500/\mu\text{L}$ and is $>1000/\mu\text{L}$ following induction or reinduction (if indicated). Time to transfusion-independent platelet recovery is measured as time from date of randomization until the first day the platelet count recovers to $>20,000/\mu\text{L}$, $>50,000/\mu\text{L}$, and $>100,000/\mu\text{L}$, without a platelet transfusion in the preceding 5 days following induction or reinduction (if indicated).

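### EFS, RFS and cumulative incidence of relapse are censored at the date last known alive, so any time with vital status only counts as relapse-free

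*Combined protocol and SAP*

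**What the plan says.** Section 9.4.2 sets the EFS rule for participants who reach CR: "Participants with induction success and no observed relapse or death events will be censored at the time they were last known to be alive". Participants without CR in the window are events at randomization.

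Table 7 (Section 8.2.2) agrees and extends the rule:
- EFS: "Participants not known to have relapsed or died will be censored on the date they were last known to be alive".
- RFS: "Participants not known to have relapsed or died at last follow-up contact will be censored on the date they were last known to be alive".
- CIR: "Participants not known to have relapsed will be censored on the date they were last known to be alive". It adds: "Participants who die without relapse will be counted as competing-risk events".

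Appendix 7 (Section 11.7) words CIR differently: "Participants not known to have relapsed will be censored on the date of last follow-up contact". It does not mention death as a competing event. Its EFS and RFS rows give no censoring rule; the RFS row reads in full "Measured from the date of randomization to date of relapse or death from any cause".

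Long-term follow-up (Section 8.2.3) has contacts every 3 months to month 24 and every 6 months after that, with the participant, a caregiver or a treating physician. Disease status with relapse date is listed for collection alongside death. A marrow examination is called for only when relapse is suspected. Section 7.4 tells sites to try to verify vital status with non-study physicians when a participant is lost to follow-up. It does not mention disease status.

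**The concern.** Knowing that someone is alive is enough to keep them at risk for death. It does not show that they are free of relapse. If the last disease information is at month 9 and a physician confirms survival at month 20, the plan credits 11 months of relapse-free time that nobody observed.

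Two things follow if such a participant relapsed in the gap. For EFS and RFS, the event is missed, or is dated late at death. For CIR, a later death is counted as death without relapse, so the relapse disappears from the numerator and reappears as a competing event.

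EFS carries its own alpha of 0.01, can open the secondary sequence alone (Section 9.4.3), and is also tested at the second interim analysis (Section 9.5). Reduced relapse is a stated expected benefit (Section 2.3.2). The only EFS sensitivity analysis that Section 9.4.2 names concerns transplant, not the censoring date.

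**Working it through.** **1. The plan's own EFS figure.** Section 9.2 gives 454 events, HR 0.7, two-sided alpha 0.01 and power above 85%. Schoenfeld: power = Φ(√d/2 × |ln HR| − z) = Φ(10.654 × 0.3567 − 2.576) = Φ(1.224) = 0.89. This agrees with the plan. The censoring rule does not enter this formula, so its effect has to be simulated.

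**2. The rules side by side.**

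| Endpoint | Section 9.4.2 | Table 7 | Appendix 7 |
|---|---|---|---|
| EFS | last known alive | last known alive | no rule |
| RFS | not given | last known alive | no rule |
| CIR | not given | last known alive; death competes | last follow-up contact; competing death not mentioned |

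Section 9.4.3 also treats death as a competing risk, so it agrees with Table 7.

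**3. Who is affected.** Induction failures are EFS events at randomization. At the assumed 50% CR rate (Section 9.2), the EFS rule touches about 0.5 × 570 = 285 participants.

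**4. Size in responders.** The documents give no share with vital-status-only follow-up, so these inputs are assumptions: control median EFS in responders 15 months (exponential), 85% of events are relapses, median 6 months from relapse to death, data cut at month 36.8, and 10-30% losing disease status but not vital status by month 24.

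True control values: 24-month EFS = 2^(−24/15) = 33.0%; 24-month CIR = 0.85 × (1 − 0.330) = 57.0%.

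| Loss in control | 24-month CIR, plan rule | CIR understated by | 24-month EFS overstated by |
|---|---|---|---|
| 0% | 57% | 0 | 0 |
| 10% | 54.6% | 2.4 points | 1.0 point |
| 20% | 52.0% | 5.0 points | 2.0 points |
| 30% | 49.3% | 7.7 points | 3.0 points |

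Separate simulation runs put the 30% CIR figure between 7.5 and 7.7 points. In the whole ITT set, the 24-month EFS error is about half the responder figure (0.5 × 1 to 0.5 × 3 = 0.5 to 1.5 points), because failures contribute no event-free time.

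**5. A second set of assumptions.** Median 18 months to relapse, 8 months from relapse to death, 100 months to death without relapse; disease information lost at a uniform 2-24 months; cut-off at 24-48 months. Control 24-month CIR is 56% with complete data. The plan rule gives 55%, 54%, 52% and 50% at 5%, 10%, 20% and 30% loss.

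**6. Hazard ratio among responders, plan rule.**

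| Loss, control / dociparstat | Complete data | Plan rule |
|---|---|---|
| Equal, 10-30% (second set) | 0.74 | 0.75 |
| 20% / 10% (second set) | 0.74 | 0.77 |
| 10% / 20% (second set) | 0.74 | 0.73 |
| 10% / 30% (first set) | 1.00; 0.70 | 0.945; 0.67 |
| 30% / 10% (first set) | 1.00; 0.70 | 1.05; 0.74 |

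With equal CR rates, failures dated at randomization would dilute these shifts in the ITT set.

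**7. Does censoring at the last disease status cure it?** Only if deaths after the gap are also censored back. With that rule, and loss unrelated to relapse, the first set returns the true 24-month values to within about 0.1 point. If event-free participants are censored back while later deaths still count, censoring becomes informative. At 20% loss in both arms, 24-month CIR is then 53.7% against 57% and a true HR of 0.70 reads about 0.71. At 10% / 30% loss, 0.70 reads 0.74-0.75, further from the truth than the current rule's 0.67.

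**The case against.** The strongest reply is that the plan already collects what is needed. Disease status is sought at the same contacts as vital status, AML therapies are recorded to last follow-up, and participants are asked to report relapse even if treated elsewhere. The two dates should normally coincide. This stands, and it makes the bias conditional.

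Four stronger readings are tempting, and the documents do not support them.

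- A reader might infer that relapse will in fact be understated. That needs a vital-status-only share, and none is given.
- A reader might infer that Section 7.3 creates vital-status-only follow-up, because it keeps in the study someone who "refuses further study-specific assessments, but agrees to collection of relevant follow-up information". Relevant follow-up information includes disease status, so this is not shown. Section 7.4 is the clearer route.
- A reader might infer that the rule tilts the EFS test toward dociparstat. With equal loss the hazard ratio barely moves, and with unequal loss it can move either way. In a double-blind trial there is no stated reason to expect a large imbalance; 10% against 30% is a stress case.
- A reader might infer that Appendix 7 conflicts on all three endpoints. It differs for CIR only, and its date may often equal the date last known alive. Its silence on competing death leaves little doubt, since Table 7 and Section 9.4.3 both specify it.

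Section 9.4 also defers detail to a SAP that is not in the supplied text and could refine the rule. Until it does, the protocol's explicit wording governs.

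**Conclusion.** The point holds as a conditional weakness in the definitions. Wherever only vital status is obtained, the written rule counts unobserved time as relapse-free, and CIR can turn an unseen relapse into a competing death. CIR is the endpoint most exposed. For EFS and RFS, a missed relapse followed by death remains an event, only later.

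Under the assumed 10-30% vital-status-only follow-up, 24-month CIR in responders is understated by about 2-7.5 points and 24-month EFS in responders overstated by about 1-3 points. The EFS hazard ratio moves by about 0.01 or less with equal loss, and by about 0.02-0.05 in either direction with unequal loss. All of this is zero if every contact yields disease status. It is worth correcting before unblinding, but it does not by itself threaten the EFS test.

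**What to change.** 1. For EFS, RFS and CIR, censor event-free participants at the last date with documented disease status. Count any contact or record that confirms no relapse, not only a marrow; marrow alone would discard most long-term follow-up.
2. State how deaths after a gap are handled. For CIR, a death after a prespecified gap (for example, more than two scheduled contact intervals) is censored at the last disease-status date and is not a competing event.
3. For EFS and RFS, apply the same gap rule to deaths and to event-free participants, and report the current rule, with all deaths counted, as a sensitivity analysis. Alternatively, keep the current EFS rule as primary and make the gap-rule analysis the sensitivity analysis.
4. Do not censor event-free participants back while still counting all later deaths.
5. Keep last known alive for overall survival.
6. Make the CIR row of Appendix 7 match Table 7, including the competing event.

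The cost is wording in Section 9.4.2, Table 7, Appendix 7 and the SAP. The data are already listed for collection. The downside is slightly less EFS follow-up and a few events censored. The gap rule also still assumes that loss of disease status is unrelated to relapse, which is why both analyses should be shown.
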